8.2.2 Rescue therapy

The threshold values are defined as follows, depending on study period:

- FPG >270 mg/dL (15.0 mmol/L) from Randomization up through the scheduled Week 8 Visit
- FPG >240 mg/dL (13.3 mmol/L) after the Week 8 visit up through the scheduled Week 12 Visit
- FPG >200 mg/dL (11.1 mmol/L) after the Week 12 Visit through the end of the 26-week Core Treatment Period
- FPG >170 mg/dL (9.4 mmol/L) or HbA1c \geq 8.0% after the Week 26 Visit through the end of the treatment period

Routine fasting SMBG (see [Section 9.2.1.6](#)) and central laboratory alerts on FPG (and HbA1c at Week 26 and onward) are set up to ensure that glycemic parameter results remain under predefined thresholds.

- If one fasting SMBG value exceeds the specific glycemic limit on one day, the patient checks it again during the two following days. If all the values in three consecutive days exceed the specific limit, the patient should contact the Investigator and a central laboratory FPG measurement (and HbA1c at Week 26 and onward) be performed as soon as possible, preferably within 7 days, to confirm the hyperglycemia.
- Upon receipt of a central laboratory rescue alert, a central laboratory re-test must be completed and confirmed as exceeding the threshold for rescue before rescue therapy is initiated. The re-test confirmation should be performed as soon as possible, but within 7 days of receipt, by unscheduled visit.

In the event that a confirmatory FPG and/or HbA1c exceeds the threshold, the Investigator should ensure that no reasonable explanation exists for insufficient glucose control and in particular that:

- The increased FPG has been tested at a fasting status (ie, no food intake for \geq 8 hours)
- Investigational medicinal product is given at the planned dose
- There is no intercurrent disease, which may jeopardize glycemic control (eg, infectious disease)
- Compliance to treatment is appropriate
- Compliance to diet and lifestyle is appropriate

If any of the above can reasonably explain the insufficient glycemic control, the Investigator should consider not initiating rescue medication and should undertake appropriate action, ie:

- Assess plasma glucose in fasting condition (ie, after at least 8 hours fast)
- Initiate an evaluation and treatment of intercurrent disease (to be reported in AE/concomitant medication parts of the e-CRF and the medical record)
- Stress the absolute need to be compliant with treatment

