- Organize a specific interview with the patient and a Registered Dietician or other qualified nutrition professional to reinforce the absolute need to be compliant with diet and lifestyle recommendations, and schedule a FPG/HbA1c assessment at the next visit.

If none of the above mentioned reasons can be found, or if appropriate action fails to decrease FPG/HbA1c under the threshold values, rescue medication may be introduced.

Initiation of open-label rescue medication(s) to treat hyperglycemia will be at the discretion of the Investigator and in accordance with local standard of care and prescribing practice. Except for SGLT2 inhibitors, any approved medication(s) including oral antidiabetic drugs or insulin can be prescribed to treat the hyperglycemia. The patient continues the study treatment (blinded) and stays in the study in order to collect efficacy and safety information. The planned visits and assessments should occur until the last scheduled visit. For patients with renal impairment, contraindications to antihyperglycemic drugs should be taken into consideration. If a patient requires glycemic rescue, the IMP received during the randomized, double-blind Treatment Period should continue and must remain blinded until the end of the study.

Rescue therapy is considered a NIMP. Rescue therapy is to be reported in the e-CRF. This information should include specific drug name, dose, route of administration, and frequency.

If not covered by health insurance, the cost of the rescue therapy will be reimbursed where permitted by local regulations.

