- Baseline BMI level ($<30, \geq 30 \text{ kg/m}^2$),
- Baseline HbA1c ($\leq 8.0\%, >8.0\%$),
- Baseline HbA1c ($\leq 8.5\%, >8.5\%$),

- Baseline mean SBP (<130 mmHg, ≥ 130 mmHg),
- Baseline eGFR (≥ 30 to <60 mL/min/1.73 m² [Moderate decrease in GFR], ≥ 60 to <90 mL/min/1.73 m² [Mild decrease in GFR], and ≥ 90 mL/min/1.73 m² [Normal]),
- Duration of diabetes (<10 , ≥ 10 years),
- Country.

The treatment effects across the subgroups defined above will be estimated for the Change from Baseline to Week 26 in HbA1c in the ITT population using the same MI method as applied to the primary analysis. The ANCOVA model will include treatment (sotagliflozin 400 mg, placebo), randomization stratum of HbA1c ($\leq 8.0\%$, $>8.0\%$), randomization stratum of SBP (<130 , ≥ 130 mmHg), subgroup factor, treatment-by-subgroup factor, and country as fixed factors and baseline HbA1c as a covariate (see sample code Part 4 of Appendix B). The adjusted estimates of treatment mean differences (sotagliflozin 400 mg versus placebo) with standard error (SE) and 95% CIs will be provided as appropriate across the subgroups. A graphical presentation of the results (ie, forest plot) will also be provided.

In the case that the subgroup factor is identical or similar to a randomization strata factor (eg, baseline HbA1c or baseline mean SBP category), only the subgroup variable (as single factor or an interaction term) will be included in the model in order to avoid the issue of collinearity in the analysis. The corresponding strata factor will not be included in the model.

Summary statistics at scheduled visits

Summary statistics (for screening value, baseline value, observed post-baseline value and its Change from Baseline) at scheduled visits will be provided for each treatment group. The summary will include the number of observations, mean, SD, standard error (SE), minimum, median, and maximum. Graphical presentations will also be used to examine trends over time using mean values (\pm SE) and mean changes from baseline (\pm SE) at each of the scheduled visits.

Similar presentations will be provided excluding measurements after rescue therapy during the entire 79-week double-blind treatment period.

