Appendix G Summary of statistical analyses

EFFICACY ANALYSIS

Endpoint	Analysis population	Primary analysis	Supportive analysis	Subgroup analysis	Other analyses
Primary endpoint					
HbA1c: Change from Baseline at Week 26	ITT	ANCOVA (with missing values imputed by the retrieved dropouts & washout imputation method or by control-based copy reference MI method under MNAR assumption): treatment, randomization stratum (HbA1c / SBP at screening), and country as fixed effects, and baseline HbA1c value as a covariate	Tipping point analysis; ANCOVA (with missing values imputed by the retrieved dropouts & washout imputation method or by control-based copy reference MI method under MNAR assumption)	Subgroups: race, ethnicity, age group, gender, baseline BMI, baseline HbA1c, baseline SBP, Baseline eGFR, Duration of diabetes, and country.	Summary statistics for observed values and changes from baseline by visit. Graphical presentations for mean changes from baseline (\pm SE) and mean values (\pm SE) by visit. By-visit summary and graph excluding measurements after rescue therapy.
Secondary endpoints					
2-hour PPG, FPG, body weight: Change from Baseline to Week 26; SBP (for patients with baseline SBP \geq 130 mmHg, all patients): Change from Baseline to Week 12	ITT	ANCOVA (with missing values imputed by the retrieved dropouts & washout imputation method or by control-based copy reference MI method under MNAR assumption): treatment, randomization stratum (HbA1c / SBP at screening), and country as fixed effects, and baseline endpoint value as a covariate	No	No	Summary statistics for observed values and changes from baseline by visit. Graphical presentations for mean changes from baseline (\pm SE) and mean values (\pm SE) by visit.

Statistical Analysis Plan

Version: 3

Lexicon Pharmaceuticals Protocol No. EFC14834

Date of Issue: 10 December 2019

Covance Study ID: 000000150525

Endpoint	Analysis population	Primary analysis	Supportive analysis	Subgroup analysis	Other analyses

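### After Week 26 the HbA1c display that drops post-rescue values retains patients according to HbA1c itself, so both arm means read too low, by an amount that depends on an unstated rescue uptake

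*SAP*

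**What the plan says.** SAP 2.4.4.1 summarises observed HbA1c and its change from baseline by arm at each scheduled visit, in tables and graphs. It then adds a second set: "Similar presentations will be provided excluding measurements after rescue therapy during the entire 79-week double-blind treatment period". Appendix G lists the same item among the other analyses of the primary endpoint: "By-visit summary and graph excluding measurements after rescue therapy". Neither place carries a caveat.

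Protocol 8.2.2 sets the rescue thresholds by period. Up to Week 26 they rest on FPG only; the last core-period step is "FPG >200 mg/dL (11.1 mmol/L) after the Week 12 Visit through the end of the 26-week Core Treatment Period". After that the trigger is "FPG >170 mg/dL (9.4 mmol/L) or HbA1c" of at least "8.0% after the Week 26 Visit through the end of the treatment period". Meeting a threshold does not start rescue. A central-laboratory re-test and a search for other explanations come first, after which "rescue medication may be introduced". The same section states: "Initiation of open-label rescue medication(s) to treat hyperglycemia will be at the discretion of the Investigator". Neither document gives an expected rescue rate.

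**The concern.** Up to Week 26 a patient leaves this display because of FPG, which is related to the plotted variable but distinct from it. After Week 26 a patient can leave because the plotted variable itself was 8.0% or more. That threshold lies inside the 7-10% enrolment range (Protocol 7.2.2), so many patients can meet it, and more of them on placebo. An observed mean over those who remain is a mean over patients selected for low HbA1c. The selection rule changes partway along a graph drawn as one trend.

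At stake is how HbA1c over the extension is read. Comparing HbA1c change at Week 79 is a stated objective (Protocol 5.3, SAP 1.2.3), and this is the only planned display of HbA1c over time without rescue-drug effects. The all-values display beside it is not a clean reference either, because rescue drugs can narrow the arm difference there.

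**Working it through.** **Plan's own figure.** SAP 1.3 supplies the SD (1.2%) and difference (0.6%) used below. SE = 1.2 × √(2/250) = 0.1073; 0.6/0.1073 = 5.59; Φ(5.59 - 1.96) = Φ(3.63) = 0.9999. The stated 99% power is reproduced. The plan gives no figure for this display, so it was simulated.

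**Inputs from the documents.** HbA1c 7-10% at Screening; SD of change 1.2%; true difference 0.60%; placebo change -0.14% (Phase 2b, 12 weeks, Protocol 4.3); visits at Weeks 26, 39, 52, 65 and 79; trigger HbA1c ≥8.0%.

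**Assumptions, not in the documents.** Baseline Normal(8.1, 0.8) truncated to 7-10; between-visit correlation of change 0.7; a confirming re-test; uptake 10-100%; no drift after Week 26 unless stated. There were 200,000 patients per arm. Only values after rescue are dropped; the triggering value stays.

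**Step 1: who meets the trigger.** At Week 26 about 52% of placebo and 35% of sotagliflozin patients are at 8.0% or above.

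**Step 2: uptake drawn afresh at each positive visit.** Displayed values at Week 79, against a true -0.14 (placebo), -0.74 (sotagliflozin) and 0.60 (difference):

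| Uptake | Retained, placebo / sotagliflozin | Placebo | Sotagliflozin | Difference |
|---|---|---|---|---|
| 100% | 30% / 48% | -1.05 | -1.39 | 0.34 |
| 75% | 35% / 52% | -0.95 | -1.32 | 0.37 |
| 50% | 44% / 60% | -0.76 | -1.19 | 0.43 |
| 25% | 63% / 75% | -0.45 | -0.99 | 0.54 |
| 10% | 82% / 88% | -0.26 | -0.85 | 0.59 |

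At full uptake the difference was 0.31-0.39 over correlations 0.5-0.9, SDs 0.9-1.2 and baseline locations 7.6-8.5. Adding an FPG trigger takes the full-uptake means to about -1.1 and -1.5.

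**Step 3: uptake as a fixed patient or site trait.** A fraction f is always rescued when positive, the rest never. With r the retention and m the mean at full uptake (Step 2, first row), the displayed mean is [(1-f) × true + f × r × m] / [(1-f) + f × r].

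- f = 0.10, placebo: (0.9 × -0.14 + 0.1 × 0.30 × -1.05)/(0.9 + 0.03) = -0.17. Sotagliflozin: (0.9 × -0.74 + 0.1 × 0.48 × -1.39)/(0.9 + 0.048) = -0.77. Difference 0.60.
- f = 0.50, placebo: (-0.070 - 0.1575)/0.65 = -0.35. Sotagliflozin: (-0.370 - 0.3336)/0.74 = -0.95. Difference 0.60.
- f = 0.75, placebo: (-0.035 - 0.2363)/0.475 = -0.57. Sotagliflozin: (-0.185 - 0.5004)/0.61 = -1.12. Difference 0.55.

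Both means fall, but the difference barely moves until f is large.

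**Step 4: upward drift of 0.6% over Weeks 26-79.** The true placebo change at Week 79 is -0.14 + 0.60 = +0.46. With 25% per-visit uptake the display shows +0.13 (difference 0.55), hiding 0.33 points of deterioration. With 50% it shows -0.21 (difference 0.44), hiding 0.67.

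**Step 5: does a model recover the truth?** Likelihood-based means from pre-rescue values, triggering value kept, returned the true arm means and difference within 0.02 in every scenario. These included removal decided by a re-test or an FPG value that was not in the model.

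**The case against.** The strongest reply is that this is a supplementary descriptive display and much of the protection is already planned. Nothing after Week 26 is tested (SAP 2.4.4), and efficacy analyses keep post-rescue values. Appendix G summarises Week 79 HbA1c from observed values and puts the excluding-rescue display under the Week 26 endpoint. The tables print the number of observations. A Kaplan-Meier curve, counts and a list of rescued patients are planned (SAP 2.4.4.3). All of this stands and limits the consequence. It does not remove the point, because those outputs show that patients leave, not that they leave because of the plotted value.

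Three stronger readings are tempting, and the documents support none of them.

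- A reader might infer that placebo must appear to improve and the effect must appear to fade. Rescue is discretionary and no uptake is stated. Under fixed partial uptake of up to one half the difference stays near 0.60%, and with drift and low uptake placebo worsens on the graph.
- A reader might infer that the durability result is wrong, and wrong against the drug. The Week 79 comparison does not rest on this display, and the sotagliflozin mean is flattered too.
- A reader might infer that missing-at-random holds by design because laboratory values trigger rescue. Judgement on compliance, diet and illness also decides it. Confirming re-tests take place at unscheduled visits, and SAP 2.5.4 uses unscheduled values only where the scheduled one is missing.

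**Conclusion.** The point holds as a limited defect in a descriptive display. After Week 26 retention depends on the plotted variable, and both arm means were biased downward in every scenario examined. Without drift, the displayed Week 79 placebo change ranged from about -0.17% (10% fixed-trait uptake) to about -1.1% (full uptake) against a true -0.14%. Sotagliflozin ranged from about -0.77% to -1.5% against -0.74%. The arm difference appears to fade to about 0.33-0.44% only when 50-100% of trigger-positive patients are rescued at each visit. With upward drift the display hides part or all of the deterioration.

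These sizes rest on the assumed baseline distribution, correlation and uptake; the direction of bias in the arm means did not depend on them over the ranges tried. No tested endpoint, no alpha and no part of the Week 26 primary analysis is affected. No view is taken on the rescue thresholds.

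**What to change.** In SAP 2.4.4.1 and Appendix G, for Weeks 39-79:

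- Present model-based means from a repeated-measures model of pre-rescue HbA1c, either replacing the observed-mean display or beside it. Include arm-by-visit, baseline HbA1c-by-visit, the randomisation strata and an unstructured covariance. Retain the value that triggered rescue; the SAP already drops only later values, and Protocol 9.1.4.1 asks for HbA1c before rescue starts.
- Print the number contributing and the cumulative number rescued, per arm, under each visit.
- Footnote that the rescue trigger changes after Week 26 and then includes HbA1c.

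The cost is SAP wording and one descriptive model, with no new data. The downside is reliance on missing-at-random, which is plausible for trigger-driven removal but not guaranteed, because investigator judgement also decides rescue.

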2.4.4.2 Analyses of secondary efficacy endpoints

For continuous secondary endpoints with missing data at baseline, missing data will be imputed using MI under the missing at random (MAR) assumption. Missing data at baseline will be imputed using regression method that includes randomization stratum of HbA1c ($\leq 8.0\%$, $>8.0\%$), randomization stratum of SBP (<130 , ≥ 130 mmHg), and baseline value in the imputation model (see sample code Part 1b or Part 2b in Appendix B).

The continuous secondary endpoints (Section 2.1.3.2) will be analyzed using similar ANCOVA model including corresponding measurements at baseline and endpoint (observed or imputed) as described in Section 2.4.4.1. The missing data at endpoint will be imputed by the retrieved dropouts & washout imputation method or by the control-based copy reference imputation method according to the criterion described in Section 2.4.4.1. After imputation, each of the complete

datasets will be analyzed by an ANCOVA model with treatment groups (sotagliflozin 400 mg, placebo), randomization stratum of HbA1c ($\leq 8.0\%$, $> 8.0\%$), randomization stratum of SBP (< 130 , ≥ 130 mmHg), and country as fixed effects, and corresponding baseline value as a covariate. For the analysis of SBP in patients with baseline SBP ≥ 130 mmHg, the randomization stratum of SBP will not be included in the ANCOVA model. Results from each complete dataset will be combined using Rubin's formula to provide the adjusted mean Change from Baseline to Week 26 (or Week 12 for SBP) for each treatment group, as well as the between-group difference (comparing sotagliflozin 400 mg vs placebo) and the 95% CI for the difference.

For all continuous secondary endpoints, summary statistics at scheduled visits will be provided for each treatment group. The summary will include the number of observations, mean, SD, SE, minimum, median, and maximum. Graphical presentations will also be used to examine trends over time using mean values (\pm SE) and mean changes from baseline (\pm SE) at each of the scheduled visits. In addition, SBP will be summarized descriptively at each visit for those with baseline SBP ≥ 140 mmHg.

The binary efficacy variables of HbA1c ($< 6.5\%$, $< 7\%$ at Week 26 respectively) will be analyzed using a Cochran-Mantel-Haenszel (CMH) method stratified by randomization stratum of HbA1c ($\leq 8.0\%$, $> 8.0\%$), and randomization stratum of SBP (< 130 , ≥ 130 mmHg). The proportion in each treatment group, as well as the difference of proportions between sotagliflozin 400 mg and placebo with associated 2-sided 95% CI will be provided. For HbA1c responders at Week 26 ($< 6.5\%$, $< 7\%$ respectively), all values at Week 26 will be used to determine whether a patient is a responder or not, even if they are measured after IMP discontinuation or rescue medication use. Patients who have no HbA1c measurement at Week 26 will be treated as non-responders. Summary tables and graphs will also be provided by treatment group at scheduled visits.

For between-group comparison, a sensitivity analysis will be performed separately for HbA1c $< 6.5\%$ responder (excluding patients with baseline HbA1c $< 6.5\%$) and for HbA1c $< 7\%$ responder (excluding patients with baseline HbA1c values $< 7\%$) by using the same CMH test as that used for the above binary variables. The summary by visit may also be provided by excluding those patients with HbA1c $< 6.5\%$ or $< 7\%$ respectively.

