7.2.2 Exclusion criteria related to diabetes history and treatment

- E 17. Hemoglobin A1c <7% or >10 % measured by the central laboratory at Screening
- E 18. Fasting plasma glucose >15 mmol/L (>270 mg/dL) measured by the central laboratory at Screening (Visit 1), and confirmed by a repeat test (>15 mmol/L [>270 mg/dL]) before randomization
- E 19. Previous use of any types of insulin for >1 month (at any time, except for treatment of gestational diabetes)
- E 20. History of diabetic ketoacidosis or nonketotic hyperosmolar coma within 12 weeks prior to the Screening Visit

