11.4.2.2 Analyses of secondary efficacy endpoints

The secondary endpoints (see [Section 9.1.2](#)) will be analyzed using a similar approach to the primary efficacy endpoint with missing values imputed by control-based multiple imputation method under the missing not at random frame work.

- For placebo patients, missing data will be imputed based on the placebo group data.
- For patients in the sotagliflozin group, missing data will be imputed as if the patients were on placebo group throughout the study.

For each of the continuous secondary endpoints, each of the complete datasets will be analyzed by an ANCOVA model with treatment groups (sotagliflozin, placebo), randomization stratum of

HbA1c ($\leq 8.0\%$, $>8.0\%$), randomization stratum of SBP (<130 mmHg, ≥ 130 mmHg), and country as fixed effects, and baseline secondary endpoint value as a covariate. Results from each complete dataset will be combined to provide the adjusted mean change from Baseline to Week 26 (or Week 12 for SBP) for each treatment group, as well as the between-group difference (comparing sotagliflozin vs placebo) and the 95% CI for the difference.

The categorical secondary efficacy variables of HbA1c $<6.5\%$, $<7\%$ at Week 26 will be analyzed using a Cochran-Mantel-Haenszel method stratified by randomization stratum of HbA1c ($\leq 8.0\%$, $>8.0\%$), and randomization stratum of SBP (<130 mmHg, ≥ 130 mmHg). The proportion in each treatment group will be provided, as well as the difference of proportions between sotagliflozin and placebo with associated 2-sided 95% CI. For HbA1c responders at Week 26 ($<6.5\%$, $<7\%$ respectively), all values at Week 26 will be used to determine whether a patient is a responder or not, even if they are measured after IMP discontinuation or rescue medication use. Patients who have no HbA1c measurement at Week 26 will be treated as non-responders.

For all secondary endpoints, summary statistics at scheduled visits will be provided for each treatment group. The summary will include the number of observations, mean, SD, SE, minimum, median, and maximum. Graphical presentations will also be used to examine trends over time using mean values (\pm SE) and mean changes from baseline (\pm SE) at each of the scheduled visits (using OC).

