1 OVERVIEW AND INVESTIGATIONAL PLAN

1.1 STUDY DESIGN AND RANDOMIZATION

This is a Phase 3, multicenter and multinational, randomized, double-blind, placebo-controlled, parallel-group study to evaluate the efficacy and safety of sotagliflozin added to metformin in patients with type 2 diabetes mellitus (T2DM) who have inadequate glycemic control on metformin.

All patients will have a Screening Period consisting of a Screening phase of up to 2 weeks and a 2-week single-blind Run-in phase prior to randomization. In order to qualify for randomization, patients must demonstrate compliance based upon pill count ($\geq 80\%$) during the Run-in phase.

Randomization will be performed via interactive response technology (IRT), where forced randomization is not allowed, and stratified by:

- Hemoglobin A1c (HbA1c) at Screening ($\leq 8.0\%$, $> 8.0\%$)
- Mean systolic blood pressure (SBP) at Screening (< 130 mmHg, ≥ 130 mmHg)

Following randomization, patients will have a 26-week, double-blind Core Treatment Period, a 53-week double-blind extension, and a 4-week post-treatment Follow-up period to collect safety information (patients who prematurely discontinue the study treatment are expected to continue in the study).

A total of 500 patients ≥ 18 years of age will be randomly assigned 1:1 to 1 of the following 2 treatment groups:

- sotagliflozin 400 mg
- Placebo

Ambulatory Blood Pressure Monitoring substudy (ABPM substudy)

Approximately 200 of the 500 enrolled patients who have a mean SBP ≥ 130 mmHg at screening are expected to participate in an ABPM substudy where patients will have blood pressure measured by a validated ABPM device.

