2 STATISTICAL AND ANALYTICAL PROCEDURES

2.1 ANALYSIS ENDPOINTS

2.1.1 Demographic and baseline characteristics

The baseline value (with the exception of serum creatinine and eGFR) is defined as the last available value before the first dose of double-blind investigational medicinal product (IMP) or the last available value prior to randomization for patients who were randomized but never exposed to IMP.

For serum creatinine and eGFR, the baseline value is defined as the average of all values before the first dose of double-blind IMP for those randomized and exposed or before randomization for those who were randomized but never exposed to IMP.

Baseline safety and efficacy parameters are presented along with the summary statistics in the safety and efficacy sections ([Section 2.4.5](#) and [Section 2.4.4](#)).

Demographic characteristics

Demographic characteristics to be summarized are:

- Age (years): Year of informed consent - Year of birth,
- Age categories: (<50, ≥ 50 to <65, ≥ 65 to <75, ≥ 75 years),
- Gender (Male, Female),
- Race (White, Black or African American, Asian, American Indian or Alaska native, Native Hawaiian or other pacific islander, Multiple, Unknown)
- Ethnicity (Hispanic or Latino, Not Hispanic or Latino, Unknown),
- HbA1c (%) at screening visit,
- Randomization strata of HbA1c ($\leq 8\%$, $> 8\%$) at screening visit (data from IRT),
- Mean SBP at screening visit,
- Randomization strata of mean SBP (< 130 mmHg, ≥ 130 mmHg) at screening visit (data from IRT),
- Baseline body mass index (BMI) (kg/m^2) derived as: (Weight in kg)/(Height in meters)²,
- Baseline BMI categories (< 30 , ≥ 30 kg/m^2),
- Country.

Disease characteristics at screening or baseline

Disease history:

- Duration of diabetes (years): (Date of informed consent – Date of diagnosis of diabetes + 1)/365.25,
- Duration of diabetes categories: (<10, \geq 10 years),
- Age at diagnosis of diabetes (years): Year of diagnosis of diabetes – Year of Birth,
- Duration of metformin treatment (years): (date of informed consent - date of first intake of metformin +1)/365.25,
- Daily dose of metformin(mg) at baseline,
- Categorized daily dose of metformin at baseline (<1500, \geq 1500 to <2500, \geq 2500 mg),
- Baseline diabetic microvascular complications (Yes, No) (ie, diabetic retinopathy, diabetic neuropathy, diabetic nephropathy, diabetic peripheral neuropathy (sensory or motor), diabetic autonomic neuropathy, and diabetic foot infection),

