In the back-up imputation method, missing post-baseline values will be imputed by control-based copy reference MI method under the missing not at random (MNAR) framework.

- For placebo patients, missing data will be imputed based on the placebo group data,
- For patients in the sotagliflozin 400 mg group, missing data will be imputed as if the patients were on placebo throughout the study, where all patients' measurements including the on-treatment measurements will be considered as if the measurements were from the placebo group in the imputation model.

Using either imputation method, missing endpoint data will be imputed multiple times to generate multiple data sets with complete data (see sample code Part 1a or Part 2a of Appendix B). The change from baseline to Week 26 will be derived from observed and imputed HbA1c values at Week 26. Each of the completed datasets after the imputation will be analyzed using the ANCOVA model with the treatment groups (sotagliflozin 400 mg, placebo), randomization stratum of HbA1c ($\leq 8.0\%$, $> 8.0\%$), randomization stratum of SBP (< 130 , ≥ 130 mmHg), and country as fixed factors, and baseline HbA1c value as a covariate (see sample code Part 4 of Appendix B). The results from each analysis will be combined using Rubin's formula, to provide the adjusted mean change in HbA1c from Baseline to Week 26 for each treatment group, as well as its between-group difference (comparing sotagliflozin 400 mg vs placebo) and the corresponding 95% confidence interval (CI) for the difference (see sample code Part 5 of Appendix B).

Sensitivity analyses

Tipping point analysis based on the same MI method as applied to the primary analysis will be performed to examine the robustness of the results from the primary analysis. Patients who were randomized to sotagliflozin 400 mg group and had no HbA1c data at Week 26 will be given a

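### The HbA1c <7% and <6.5% comparisons use a valid CMH test on the two screening strata but leave out continuous baseline HbA1c, giving up a modest amount of precision

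*SAP*

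**What the plan says.** SAP 2.4.4.2 states that the two responder variables "will be analyzed using a Cochran-Mantel-Haenszel (CMH) method stratified by randomization stratum of HbA1c"; the sentence then adds the SBP stratum, so there are four cells. Protocol 11.4.2.2 agrees ("will be analyzed using a Cochran-Mantel-Haenszel method stratified by randomization stratum of HbA1c", again with SBP), as does SAP Appendix G. The HbA1c stratum is the value described in SAP 1.1 as "Hemoglobin A1c (HbA1c) at Screening", cut at 8.0%. The SBP stratum is the screening mean cut at 130 mmHg.

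Patients with no Week 26 HbA1c count as non-responders. One sensitivity analysis repeats the same CMH test after removing patients whose baseline HbA1c is already below the relevant cut.

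The primary ANCOVA in SAP 2.4.4.1 uses treatment, the same two strata, "and country as fixed factors, and baseline HbA1c value as a covariate (see sample code Part 4 of Appendix B"). Under SAP 2.4.4.2 each continuous secondary endpoint also adjusts for its own baseline value. Baseline, in SAP 2.1.1, "is defined as the last available value before the first dose of double-blind investigational medicinal product (IMP"), and Protocol 10.1.2.1.1 schedules an HbA1c sample on Day 1.

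In SAP 2.4.4.5, HbA1c <7.0% is the last step of the fixed sequence, tested two-sided at 0.05. HbA1c <6.5% is outside the sequence.

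**The concern.** Protocol 7.2.2 excludes patients with "Hemoglobin A1c <7% or >10 % measured by the central laboratory at Screening". One HbA1c stratum therefore spans 7.0-8.0% and the other runs from above 8.0% to 10.0%. A patient entering at 7.1% is far more likely to finish below 7% than one entering at 7.9%, yet the CMH test treats them alike. The same holds for 8.1% and 9.9%. The Day 1 value, closer to treatment than the screening value, carries that within-stratum information and is already in the database.

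The responder comparisons are thus the only formally tested efficacy endpoints that make no use of a continuous baseline value. At stake is the width of two confidence intervals and the chance of passing the last gated test, for which the documents state no power.

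**Working it through.** **The plan's own figure.** Protocol 11.1 gives 250 per arm, SD 1.2, difference 0.6, two-sided 0.05 and at least 99% power for the primary endpoint. The standard error is 1.2 × √(2/250) = 0.1073, and 0.6/0.1073 = 5.59. Power is Φ(5.59 − 1.96) = Φ(3.63) = 0.9999, so the statement reproduces. For 99% power, 147 per arm would do. No stated figure is disputed here.

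**Inputs from the documents.** 250 per arm, 1:1; SD of change 1.2 and difference 0.6 (Protocol 11.1); placebo change −0.14 (Phase 2b result, Protocol 4.3); screening HbA1c 7-10%; strata cut at 8.0% and 130 mmHg; missing counted as non-response.

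**Assumptions not in the documents.** Screening HbA1c centred at 8.2, SD 0.85 before truncation; measurement error SD 0.25 per visit; half the patients in each SBP stratum, SBP unrelated to HbA1c; 10% missing (5% and 20% also run); slope of Week 26 on baseline 0.7 to 1.0 (correlation about 0.39 to 0.67). SD of change 1.0 and 0.8 and a true difference of 0.35 were also run.

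**Comparison.**
- Planned: the stratified difference Σw(p₁ − p₀)/Σw over the four strata, with w = n₁n₀/(n₁ + n₀).
- Alternative: logistic regression on treatment, both strata and continuous baseline HbA1c. The standardised risk difference is the average over all patients of predicted response on sotagliflozin minus predicted response on placebo.
- Variance reduction: 1 − (SE adjusted / SE CMH)².

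There were 1,200 to 4,000 simulated trials per scenario. SEs are mean model-based values. Reductions come from unrounded SEs. For example, the rounded values in row 5 give 1 − (0.0322/0.0334)² = 7.1%, against 7.5% unrounded.

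| Cut | SD | Slope | True diff. | Missing | Response, placebo / sotagliflozin | SE, CMH / adjusted | Variance reduction | Power, CMH / logistic |
|---|---|---|---|---|---|---|---|---|
| <7% | 1.2 | 0.7 | 0.6 | 10% | 16.6% / 30.0% | 0.0362 / 0.0357 | 2.9% | 95.6% / 96.5% |
| <7% | 1.2 | 0.85 | 0.6 | 5% | 18.6% / 32.3% | 0.0370 / 0.0361 | 4.6% | 95.2% / 96.3% |
| <7% | 1.2 | 0.85 | 0.6 | 20% | 15.6% / 27.3% | 0.0352 / 0.0345 | 3.5% | 90.9% / 92.3% |
| <7% | 1.0 | 1.0 | 0.6 | 10% | 15.8% / 29.6% | 0.0348 / 0.0335 | 7.4% | 96.8% / 97.7% |
| <7% | 1.0 | 1.0 | 0.35 | 10% | 15.9% / 23.4% | 0.0334 / 0.0322 | 7.5% | 59.7% / 63.6% |
| <7% | 0.8 | 1.0 | 0.6 | 10% | 13.0% / 27.7% | 0.0328 / 0.0312 | 9.9% | 99.3% / 99.8% |
| <6.5% | 1.2 | 0.7 | 0.6 | 10% | 8.9% / 18.4% | 0.0296 / 0.0293 | 2.0% | 87.7% / 88.5% |
| <6.5% | 1.2 | 1.0 | 0.6 | 10% | 10.7% / 20.4% | 0.0308 / 0.0301 | 4.6% | 87.6% / 89.1% |
| <6.5% | 1.0 | 1.0 | 0.6 | 10% | 8.1% / 17.9% | 0.0283 / 0.0275 | 5.9% | 92.8% / 93.9% |

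The SD 0.8, slope 1.0 row is the most favourable corner, and it lies outside the plan's SD.

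**In interval terms.** Row 1: the half-width goes from 1.96 × 0.0362 = 7.1 points to 1.96 × 0.0357 = 7.0 points. Row 5: from 1.96 × 0.0334 = 6.5 to 1.96 × 0.0322 = 6.3 points.

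**Type I error at <7%, two-sided.** CMH 0.048-0.049, logistic test 0.050-0.052 (2,500 null trials per scenario). Both are consistent with 0.05.

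**Other assumed entry distributions.** Centring screening HbA1c at 8.1 with SD 0.9 gave reductions of 3.9-6.6% for <7% and 2-5% for <6.5%. Point estimates agreed (for example 14.5 points by both methods). A further run with 10% missing gave about 3-8% and about 4%, with power for <7% moving from about 93% to 95% at SD 1.2.

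**The case against.** The strongest reply is that nothing is broken. CMH stratified by the randomisation factors is valid, protocol and SAP agree, and continuous HbA1c is already analysed efficiently as the primary endpoint. The responder test is a dichotomy of that same outcome. It sits last in the sequence, so no later test depends on it, and <6.5% supports no confirmatory claim. All of this stands, and it keeps the point small.

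Four stronger readings are tempting, and the documents do not support them.
- **That the test adjusts for screening HbA1c alone.** It is also stratified by screening SBP. That factor was simulated as unrelated to HbA1c and so recovered no precision.
- **That baseline HbA1c is ignored for responders.** The planned sensitivity analysis uses it to exclude patients. It is not a covariate adjustment, however. Under the assumptions above only about 2.8% of patients start below 7% (0.028 × 500 = 14), so it leaves the spread among the rest untouched.
- **That the trial could have been smaller.** Its size is set by the primary endpoint, which already has ample power, so no patients would be saved.
- **That the change is free.** CMH is written into the protocol, so replacing it in the gated test is a departure to be documented. A standardised difference also needs a variance method and a fallback, which the CMH test does not.

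**Conclusion.** The point holds as an optional improvement in efficiency. Leaving continuous baseline HbA1c out of the responder comparisons gives up about 3-8% of variance for <7% (near 10% in the most favourable corner) and 2-6% for <6.5%. At the planned SD and difference that is about 1-2 points of power. With a true difference of 0.35 the gain for <7% was about 1.5-5.5 points.

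The direction was the same in every scenario run. The size depends on the assumed baseline spread, measurement error, slope and missingness, since the documents give no responder rates, baseline SD or correlation between baseline and Week 26. A reader might infer that the planned test is biased or invalid. It is not: its error rate is kept and the point estimates agree.

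**What to change.** Before unblinding, add to SAP 2.4.4.2 a logistic regression for HbA1c <7% and <6.5% with treatment, both randomisation strata and continuous baseline HbA1c. Report the standardised risk difference with a 95% CI by a named variance method, for example the delta method or bootstrap. Keep missing as non-response.

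Preferably make this the gated <7% test, state exactly which statistic is tested, keep CMH as the sensitivity analysis, and record the change from Protocol 11.4.2.2. The two-sided error rate above was obtained for the logistic test, so it should be confirmed for the standardised difference with the chosen variance method. If the sponsor prefers not to change the gated test, add the model as a pre-specified supportive analysis.

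The cost is one extra model, a documented protocol departure if the gate changes, and a stated fallback to CMH if <6.5% responders are too sparse. No new data are needed.

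Possible wording: *The proportions with HbA1c <7% and <6.5% at Week 26 will be compared by the standardised risk difference from a logistic model with treatment, both randomisation strata and continuous baseline HbA1c, with a 95% CI by [method]. If the model for <6.5% cannot be fitted, the stratified CMH analysis will be used.*
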